10.3 General

Demographics: The demographics form collects information about demographic characteristics of the study candidate, including date of birth, sex, racial/ethnic group, educational level, marital status, and employment status. The demographics form will be completed once at enrollment for both Full and Limited Study participants.

Locator Information Form: A locator form is used to obtain information to assist in finding patient-participants during follow-up. This form collects the participant's current address, email address, and phone numbers. In order to facilitate locating participants if direct contact efforts are unsuccessful, addresses and phone numbers of family/friends who may know how to reach the participant are collected, as well as information such as social security number, driver's license number and other information to aid in searches of public records. Two valid contacts are required for study eligibility. This information will be collected at baseline and updated at the Day 30 follow-

up for Full Study participants only. Data entered in this form will be encrypted and will not be used in data analyses.

Other Substance Use: Selected questions from the Alcohol, Smoking and Substance Involvement Screening Test (ASSIST)-lite [18] will be used to assess drug and alcohol use over the past 3 months and will be asked at baseline for Full Study participants only.

PROMIS-29: Health-related quality of life (HRQoL) will be measured using the Patient-Reported Outcomes Measurement Information System (PROMIS).[19, 20] PROMIS was developed using item response theory, with support from the NIH. Because of its foundation, PROMIS is able to improve upon common deficiencies of existing, widely-used, HRQoL instruments capable of generating a single health utility index value for the calculation of QALYs [21-24] including: floor and ceiling effects among participants who are especially ill or healthy, respectively, and imprecise questions that blend concepts.[25] The PROMIS-Preference (PROPr) scoring system uses the respondent's scores for each of the following PROMIS domains to calculate a health utility index value that represents the general US population's preference for the respondent's current health state: Cognitive Function–Abilities, Depression, Fatigue, Pain Interference, Physical Function, Sleep Disturbance, and Ability to Participate in Social Roles and Activities.[26, 27] PROMIS has 5 levels for each domain: no problems, slight problems, moderate problems, severe problems, and extreme problems. The health-utility value produced by PROPr can range from -0.022 to 1, where 0 represents death, 1 represents perfect health, and values below 0 represent states perceived to be worse than death. Construct validity for PROPr has been demonstrated using other HRQoL instruments and two large datasets from the general US population.[25] The health-utility value is then used to calculate QALYs, as our team, and many others have done in similar studies.

Motivations, Attitudes and Expectations: Motivation for participating in the study and attitudes and expectations regarding medication treatment for OUD are collected once at baseline for Full Study participants.

Study Completion: This form tracks the participant's status in the study through the Day 30 visit. It is completed for both Full and Limited Study participants after completion of the Day 30 follow-up or once the visit window lapses for participants who do not complete the Day 30 follow-up. This form is used in data analyses to address variables such as treatment retention and completion. This form also provides a location for the site PI attestation of review of all study data entered in eClinical.

10.4 Health Services

Health Services Utilization Inpatient and Health Services Utilization Outpatient: A brief, structured interview regarding health care utilization (inpatient and outpatient) will be used, which collects information on the type and amount of services received. This includes ED visits, hospitalizations, primary medical care visits (excluding those for buprenorphine treatment and 12-step group sources of support (e.g., Narcotics Anonymous). It is completed at baseline and at the Day 30 follow-up visit for Full Study participants only.

Healthcare Visit Logistics: The Healthcare Visit Logistics form collects information on distance to healthcare providers (e.g., how many miles patient-participants drive to providers). This form is completed once at baseline for Full Study participants.

Health Status: The Health Status form collects information on HIV and Hepatitis C status, pain (PEG), and psychological health (PHQ-9), usual care and reason for the ED visit. Health status

questions are collected at baseline and the Day 30 follow-up visit for Full Study participants. The Mental Health Assessment form is triggered if the participant responds that they have had “Thoughts that you would be better off dead, or of hurting yourself in some way” over the past two weeks in the PHQ-9 section of the form.

ED Visit Review: The ED Visit Review form collects information about the index ED visit including enrollment date, discharge date and time, chief complaint, critical actions completed, and discharge diagnosis. It is completed by research staff via medical chart review and without participant input for both limited and Full Study participants.

ED Visits and Hospitalizations: The ED Visits and Hospitalizations form collects information about the index ED visit and any visits or hospitalizations at the site between the index visit and follow-up. It is completed at the Day 30 follow-up visit. Data are gathered by research staff via medical chart review and without participant input for both Limited and Full Study participants.

10.5 Process Outcomes

Engagement in Treatment Survey: At the Day 30 follow-up visit Full Study participants will be asked to report whether they are engaged in formal addiction treatment. Data will be reported on the Engagement in Treatment: Patient survey. The outcome will be confirmed with the addiction treatment provider using the Engagement in Treatment: Facility survey, which includes the type of treatment the participant is receiving, i.e., methadone, buprenorphine and/or naltrexone treatment, detoxification, inpatient or outpatient treatment. Date of admission is recorded as well as the level of treatment received according to ASAM Levels of care, such as Level I: Outpatient Treatment; Level II: Intensive outpatient treatment (including partial hospitalization); Level III: Clinically managed residential/inpatient treatment; Level IV: Medically managed intensive inpatient treatment or Other-specified. Engagement in Treatment: Facility survey will be completed with both Full and Limited Study participants. ED visit is considered Day 0; Engagement is assessed on Day 30.

Prescription Drug Monitoring: The states’ Prescription Drug Monitoring Programs will be accessed to identify all opioid prescriptions that participants fill during the follow-up period (date of ED discharge through Day 30). This form will be completed once at the Day 30 visit for both Full and Limited Study participants. This form is completed via database review and without participant input.

Treatment Satisfaction/Acceptability: This form will be completed at the Day 30 follow-up visit for Full Study participants. This form will collect information on satisfaction with and acceptability of OUD treatment received throughout the study.

Treatment Effectiveness Assessment: This form will be completed at the baseline and Day 30 follow-up visit for Full Study participants. This form collects self-report data across four domains: substance use, health, lifestyle, and community.

10.6 Opioid Outcomes

Timeline Follow-Back (TLFB): The Timeline Follow-Back[28] procedure will be used to elicit the Full Study participant’s self-reported use of illicit substances at baseline and throughout study participation. The TLFB will be administered at baseline for the 7-day period prior to the index ED visit. At the Day 30 follow-up visit the assessment period will be the 7 days preceding the Day 30 post index ED visit.

Overdose Events and Risk Factors: We will ask Full Study participants about opioid-related overdose events, overdose prevention, and overdose risk factors. This form will be completed at baseline and at the Day-30 follow-up visit for Full Study participants only.

Urine Drug Screen: Urine testing will be performed for the presence of the following drugs: opioids, oxycodone, PCP, benzodiazepines, cocaine, methamphetamine, amphetamine, 3,4-methylenedioxy-methamphetamine (MDMA), tetrahydrocannabinol (THC), barbiturate, methadone, fentanyl, and buprenorphine. The urine drug screen is conducted by research staff for research purposes only. UDS results will not be entered into the medical chart. The UDS is performed at baseline and the Day 30 follow-up visit for Full Study participants. Urine testing supplies will be provided to the sites.

Overdose Events and Risk Factors: The Overdose Events and Risk Factors form is completed at baseline and Day 30 for Full Study participants. This self-report form collects information on overdose risk, experience with Naloxone, and past 30-day opioid overdose events.

10.7 Safety

Mental Health Assessment: The Health Status form contains a question that asks participants if they have had “thoughts that you would be better off dead, or of hurting yourself in some way” over the past two weeks. For “in-person” research visits (i.e., either on site or in the field where clinician assessment resources are reasonably available), any response other than “Not at all,” will prompt a clinician assessment for suicide risk and trigger a requirement for the completion of the “in-person” version of the Mental Health Assessment form by the RA. The Mental Health Assessment form documents the performance of the required direct clinician evaluation of the participant for suicide/homicide risk according to the site-specific SOP. This clinician evaluation should take place prior to the participant leaving the study site. A protocol deviation is required if the clinician evaluation is not completed prior to the participant leaving the study site for in person research visits. For participant research visits *not* conducted in person or in a location that is physically remote from reasonably available clinician assessment resources, the “remotely” version of the Mental Health Assessment form should be completed to document provision of national or local mental health resource referral/contact information to the participant. A protocol deviation is required if these referral/contact information resources are not provided to the participant prior to the participant leaving the remote visit site. The Mental Health Assessment form is not completed when suicidality/homicidality is not endorsed on the respective Health Status form question (e.g. spontaneously reported by a participant). In these cases, the assessment of reported suicidality/homicidality will be conducted in accordance with the study site’s standard of care procedures. Consequently, all sites should monitor participant responses to the Health Status form, as well as spontaneous expression of potential participant suicidal/homicidal ideation, and have procedures in place to ensure participant safety.

Opioid non-fatal overdose events, healthcare utilization including ED visits and hospitalizations, suicidal ideation, and all deaths including fatal overdoses will be tracked beginning at the time of consent and ending with participant study completion at the Day 30 visit. Overdose events since enrollment will be captured by participant self-report, potentially collateral report (e.g., family), review of health records and EMS records (pending availability). In the event of Full Study participant withdrawal/loss to follow-up and in the case of all Limited Study participants, we will attempt to track fatal overdose events and other mortality through Offices of Vital Statistics, Offices of the Certified Medical Examiner, and/or local morgues. Overdose events will be recorded on the Overdose Events and Risk Factors form. Research staff may become aware of safety events in between study visits (i.e., via participant family and friends, ED visits, etc.). These non-fatal events should be recorded on a study progress note to prompt data entry of the event at the

next research visit. Deaths will be entered into the database in real time, as staff become aware of the event. Since BUP is provided consistent with community practice, a medication adverse event profile will not be maintained. Each facility has SOPs to address safety events including overdose and suicidality and other psychiatric emergencies, and these will be followed. When a medical or psychiatric emergency is identified, including presence of potential suicidal ideation, research staff will activate local procedures to ensure participant safety. As there is no planned interaction between Limited Study participants and research staff post enrollment, research staff will not actively intervene when safety events are identified in Limited Study participants.

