ED patients who are candidates for ED-initiated BUP (and who meet the additional study eligibility criteria to become research participants) may be enrolled as Full Study or Limited Study participants. Full Study participation involves two in-person research visits occurring ideally at the index ED visit and 30 days after ED discharge, as in the parent study. In addition, consenting participants will be asked to authorize study staff to perform a data match with health and administrative data pending data use agreements for a period beginning 1 year prior to study enrollment and ending 2 years following study enrollment. Limited Study participation will be offered to candidates who meet criteria for ED-BUP candidacy but do not meet all of the eligibility criteria (e.g., inadequate locator information) for Full Study participation. Limited Study participation includes completion of screening assessments and data matching only, without active participation in the baseline and day 30 research visits. In addition, a Waiver of Consent/HIPAA Authorization is requested to perform data matching for all adult ED patients who screen positive for non-medical opioid use during the study data collection period. Analyses will also be conducted for subgroups, including those determined to be candidates for BUP and/or receive medication for OUD, among others.

We will also recruit ED staff, patients, and other stakeholders and key informants to be participants in qualitative interviews and/or focus groups at the close of study for the purpose of learning about patient-, provider-, and organizational-level barriers and facilitators to adoption and sustainability. These data (along with qualitative data collected through CTN-0069 and CTN-0079) will provide context to study outcomes and allow us to more comprehensively address our primary research question.

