9.4 Research Participant Procedures

9.4.1 Full Study Participants

Patients who are determined to meet Full Study eligibility criteria (section 7.2) will be invited to participate in the Full Study, which consists of two research visits and providing authorization for research staff to access their health records and to link/match their Protected Health Information (PHI) and Personally Identifiable Information (PII) to administrative data (e.g., PDMP, claims) for a period beginning 1 year prior to study enrollment through 2 years following study enrollment. As described in the Manual of Operations (MOP), the baseline research visit will ideally occur at the index ED visit or within 72 hours of ED discharge, but recruitment efforts may continue for up to 7 days post discharge. The Day 30 follow-up visit (30 days post ED discharge) will ideally occur no more than 7 days after this target, although outreach to reengage participants lost to contact may continue past this point.

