2.0 OVERSIGHT OF CLINICAL RESPONSIBILITIES

A. Site Principal Investigator

Each participating site's Principal Investigator (PI) is responsible for study oversight, including ensuring human research subject protection by designating appropriately qualified, trained research staff to assess, report, and monitor safety events.

Because this prospective study will examine BUP initiation, and the use of this medication is in line with community practice, safety reporting will be limited to recording opioid non-fatal overdose events, healthcare utilization including ED visits and hospitalizations, suicidal ideation, and all deaths including fatal overdoses will be tracked within the 30 days between the index ED visit and Day 30.

These safety events occurring during the course of the clinical trial will be collected, documented, and reported by the investigator or sub-investigators according to the Protocol. Since BUP is

provided consistent with community practice, a medication adverse event profile will not be maintained.

Non-fatal opioid overdoses will be assessed at each visit during the study and collected on the Overdose Events and Risk Factors form. Safety events resulting in death including fatal overdoses are required to be entered into the adverse/serious adverse event form set in the data system within 24 hours of site's knowledge of the event. The other safety events will be reported on study specific forms.

B. CCC Safety Monitor/Medical Monitor

The NIDA CTN Clinical Coordinating Center's (CCC) Safety Monitor/Medical Monitor or designee is responsible for reviewing all adverse events and serious adverse events reported. The CCC Safety Monitor/Medical Monitor is alerted via email each time an SAE is reported in the EDC. All SAEs will be reviewed at the time they are reported in the EDC. The Safety Monitor/Medical Monitor or designee will also indicate concurrence or not with the details of the report provided by the site PI. Where further information is needed, the Safety Monitor/Medical Monitor or designee will discuss the event with the site staff. Reviews of SAEs by the CCC Safety Monitor/Medical Monitor or designee will be documented in the Advantage eClinical data system and will be a part of the safety database. All AEs are reviewed on a weekly basis to observe trends or unusual events.

Voluntary Regulatory Reporting in non-IND Trials:

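### Non-fatal safety events learned between visits wait on a progress note for the Day 30 visit, and no entry trigger is stated for Full Study participants who never complete it

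*Combined protocol and SAP*

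**What the plan says.** Section 10.7 sets two entry rules. For non-fatal events that staff hear of between visits (from family, an ED visit and so on): "These non-fatal events should be recorded on a study progress note to prompt data entry of the event at the" next research visit. For deaths: "Deaths will be entered into the database in real time, as staff become aware of the event". Appendix A, section 2.0 A, adds a 24-hour limit for deaths.

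The synopsis (2.4) fixes the number of visits: "Full Study participation involves two in-person research visits occurring ideally at the index ED visit and 30 days after ED discharge". Section 9.4.1 gives the timing. Baseline can be late, since "recruitment efforts may continue for up to 7 days post discharge", and "The Day 30 follow-up visit (30 days post ED discharge) will ideally occur no more than 7 days after this target", with outreach allowed beyond that.

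For Full Study participants who withdraw or are lost, and for all Limited Study participants, section 10.7 says "we will attempt to track fatal overdose events and other mortality" through vital-statistics and similar offices. It has no matching sentence for non-fatal events.

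On review, Appendix A, section 2.0 B, says "All AEs are reviewed on a weekly basis to observe trends or unusual events". Section 13.14.2, which names Safety Events, says only that review is regular and gives no interval.

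Section 10.3 has the Study Completion form filled in after Day 30, or "once the visit window lapses for participants who do not complete the Day 30 follow-up".

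**The concern.** Non-fatal overdose and suicidal ideation are two of the few events this study tracks (13.14.3). The medical monitor is to review all Safety Events and decide which need expedited reporting (13.14, 13.14.2). An event that sits on a site progress note cannot be screened centrally.

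The rule makes entry of a known event depend on the participant coming back. Participants who overdose may be less likely to return, so the loss could fall most heavily where events are most common. Section 12.12 summarises events by site, so different Day 30 attendance across the three sites could also look like different event rates. Section 14.4 asks for eCRFs to be completed on an ongoing basis, which fits poorly with holding known events.

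**Working it through.** The documents state no reporting delay and no Day 30 attendance rate, so there is no figure of theirs to reproduce. Three checks follow.

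**1. How long a known event can wait.** Let *b* be the baseline day (0 to 7, section 9.4.1), *v* the Day 30 visit day (30 to 37, same section) and *t* the day staff learn of the event. The wait is *v* − *t*. Assume *t* is uniform from *b* to 30; this is an assumption, not a document figure. The range is then (*v* − 30) to (*v* − *b*), and the mean is *v* − (*b* + 30)/2.

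| Baseline day | Visit day | Range (days) | Mean (days) | Held over 7 days | Held over 14 days |
|---|---|---|---|---|---|
| 0 | 30 | 0–30 | 15 | 23/30 = 77% | 16/30 = 53% |
| 0 | 37 | 7–37 | 22 | 100% | 23/30 = 77% |
| 7 | 30 | 0–23 | 11.5 | 16/23 = 70% | 9/23 = 39% |
| 7 | 37 | 7–30 | 18.5 | 100% | 16/23 = 70% |

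An event learned on Day 2 waits 28 to 35 days. Outreach can run past Day 37, so 37 is not a hard upper limit.

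**2. What happens if Day 30 is never completed.**

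- *Non-fatal overdose, Full Study.* Section 10.7 sends it to the Overdose Events and Risk Factors form. Section 10.6 describes that form as self-report, completed at baseline and Day 30. Section 10.7 also lists collateral report, health records and EMS records (pending availability) as sources, but a source is not an entry trigger.
- *Suicidal ideation, Full Study.* It comes from the Health Status form at visits. Section 10.7 says the Mental Health Assessment form is not completed for spontaneous reports.
- *ED visits and hospitalisations.* Section 10.4 abstracts these from the chart without the participant, but only for visits at the study site. Off-site care has no such route.
- *Limited Study.* Table 3 schedules Safety Events at Day 30, and section 9.4.2 completes post-enrolment assessments from charts or available data, so no visit is needed. Table 3 does not schedule the Overdose form for them.

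The gap without a trigger is therefore known overdose, suicidal ideation and off-site care in Full Study participants who never complete Day 30.

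**3. What the rule could cost the overdose count.** Only the 120 Full Study participants (7.2.2) is a document figure. The rest is assumed: 10%, 20% or 30% miss Day 30; non-fatal overdose occurs in 5% of attenders and 15% of non-attenders; staff learn of half the events in non-attenders; all events in attenders are captured; nothing is recovered from records.

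| Miss Day 30 | True events | Entered under the rule | Entered on awareness | Cost of the rule |
|---|---|---|---|---|
| 10% (12) | 108×0.05 + 12×0.15 = 5.4 + 1.8 = 7.2 | 5.4 (75%) | 5.4 + 0.9 = 6.3 (88%) | 0.9/7.2 = 13 points |
| 20% (24) | 96×0.05 + 24×0.15 = 4.8 + 3.6 = 8.4 | 4.8 (57%) | 4.8 + 1.8 = 6.6 (79%) | 1.8/8.4 = 21 points |
| 30% (36) | 84×0.05 + 36×0.15 = 4.2 + 5.4 = 9.6 | 4.2 (44%) | 4.2 + 2.7 = 6.9 (72%) | 2.7/9.6 = 28 points |

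Only the last column belongs to the entry rule. The remaining shortfall is events that staff never learn of, which no entry rule recovers.

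**The case against.** The strongest reply is that section 10.7 does not forbid entry when Day 30 is missed. The note exists to prompt entry, outreach may continue past Day 37, and section 10.7 allows for visits that are not in person. A reader might infer that known events in non-attenders are never entered. The text does not support that: it states no trigger or deadline, which is a gap and not a bar. It is still more than silence, because the one instruction given ties entry to a visit that may not take place.

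A reader might also infer that Limited Study participants have no route at all for non-fatal events. Table 3 and section 9.4.2 show that they do, apart from the Overdose form.

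Nor can the delay be measured against a settled weekly review. Appendix A gives a weekly interval for AEs, while section 13.14.2 gives none for Safety Events, and section 13.14 says AEs other than Safety Events are not tracked. Delay is also not weeks in every case, since events learned near Day 30 may be entered almost at once.

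Finally, the consequence is bounded. The safety analysis is a descriptive summary in a study that Appendix A calls minimal-risk and observational. Non-fatal events also go to the IRB under its own guidelines (13.14.3). The MOP and local SOPs, which are not in the documents, may add detail. These points limit the size of the problem but do not supply the missing trigger.

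**Conclusion.** The point holds in this form. Followed as worded, section 10.7 delays central sight of known non-fatal events by 0 to about 37 days. It also leaves no stated entry trigger for known overdose, suicidal ideation or off-site care in Full Study participants who never complete Day 30. The mean waits rest on uniform learning times.

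The effect on the section 12.12 counts cannot be sized from the documents. The 13 to 28 points (about 1.8 of 8.4 events at 20% non-attendance) depend wholly on the stated assumptions and would be smaller with any recovery from records. It is tempting to read the recorded shares of 75% down to 44% as the harm done by the rule, but that would charge it with events staff never knew of.

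The entry rule does not affect emergency response. Section 10.7 has local procedures activated when an emergency is identified, and its separate provision that staff do not actively intervene for Limited Study participants does not turn on data entry.

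**What to change.** In section 10.7, replace the progress-note rule with wording such as: *Non-fatal safety events are entered on the study-specific form, with event date and source (participant, collateral, chart, EMS), when staff become aware of them. Any event still on a progress note is entered when the Study Completion form is completed, including when the visit window lapses.* State which form receives a known non-fatal overdose in a Limited Study participant.

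Reconcile the review interval in section 13.14.2 with that in Appendix A, section 2.0 B, using one term for the events covered.

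Both mechanisms already exist in the plan: real-time entry for deaths, and a Study Completion form for non-attenders. The cost is a short replacement in 10.7, a line in the MOP and opening the eCRF for unscheduled entry, with no added visits. The downside is some duplicate entries to reconcile with Day 30 self-report, which the event date and source fields would help to resolve. The change concerns data entry only.
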